Descriptive statistics were used to summarize the demographic and other characteristics of participating children. Categorical variables were described with frequencies and percentages, normally-distributed continuous variables as mean $\pm$ SD and non-normal continuous variables as median and interquartile range (25th-75th percentiles). Box plots were used to visually inspect the biomarker data. For data below LOD, imputation was performed based on existing suggestions for handling non-detect data. For 6-CN and 3-PBA, the percentage of data below LOD was 72% and 23% accordingly, so the imputation was performed using the regression on order statistics (ROS). For MDA and creatinine, the percentage of data below LOD was very low ( $\approx$  1%), so the LOD/2 imputation was used. The baseline characteristics were compared between the study groups with t-test for the normal continuous variables or Wilcoxon test, and chi-square for the normal, non-normal, and for the categorical variables, respectively.

The percent change between the baseline (last sample of conventional treatment before the start of the organic treatment) and after 40 days of organic diet (last sample of organic treatment) was determined with one sample t-test for all biomarkers (log-transformed) and the change between the conventional and organic treatment (medians) was determined using Wilcoxon test for all biomarkers (non-normal variables).

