variable used for the estimation of the sample size was a biomarker of inflammation (C-reactive protein), because the biomarkers of inflammation/oxidative stress were one the primary outcomes for the trial and we information on pesticide levels were unavailable at that time. The lack of pertinent human studies with similar setting and characteristics to the present study that involved exactly the same biomarkers of effect (8-OHdG and isoprostanes) led us to use the available human study of CRP.⁷

The input parameters were: significance level, within patient standard deviation or standard deviation of the difference between the two values for the same patient, power and minimal detectable difference in means. Based on the literature, the within subject standard deviation of CRP was assumed to be 0.5,⁷ and we hypothesized a minimal detectable difference in biomarkers of effect (CRP) between the organic and conventional treatment to be 0.1, based on other intervention studies.⁸⁻¹⁰ Assuming a power of 80% and a two-sided 5% significance level, the sample size for this two-treatment crossover study was estimated to be 200 children. The clustering was not addressed, but the within cluster within period and the within cluster between period intra cluster correlation estimates were assumed equal.

Statistical analysis

General principles

Participant population

The analysis population consists of all children excluding withdrawn children whose parents also withdrew their consent for the data to be used or children who left the trial with less than 12 days in the organic diet arm and did not provide any samples during the organic diet intervention.

Whilst it was not anticipated that there would be children who cross-over their trial group (i.e. change from intervention to control, or vice versa), any two exceptions were documented. Two children (following their parents' signed consent) decided to enroll in the study after the study was initiated and at the end of the conventional arm, right before the beginning of the organic diet treatment, based on their school's group (Group 2). These children provided a baseline sample, 2 or 3 samples during the organic period and 2 conventional samples after the organic diet period ended, so they basically followed the opposite design based on their school. However, they did follow the

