organic period at the same time as their classmates. These two children were allocated to Group 1 for analysis purposes. There was no issue of transferring knowledge within the school about the organic diet intervention from these two children since they were participating in the intervention arm at the same time the rest children of the school were. The only difference was that these two children participated in the conventional arm after the end of the organic diet and not before the beginning of the organic diet treatment, as the rest of the children of their respective school.

The full analysis population consists of all children who followed the organic treatment for at least 12 days and provided at least one urine sample during the organic diet intervention.

Levels of confidence and p values

Statistical tests and confidence intervals were two-sided. 95% confidence intervals will be presented wherever possible. The statistical significance level set will be at the 5% level.

Unadjusted and adjusted analyses

All outcomes were used with for creatinine levels to account for urine dilution. If outcomes are not normally-distributed and the analyses require the normality assumption, then outcomes will be log-transformed (natural logarithm).

Multiple testing

Multiple testing will be accounted for, using the Benjamini-Hochberg (false discovery rate, FDR) method considering all the regression parameters of the primary and post-hoc analyses. Q-value <0.05 indicates statistical significance of an association after controlling the false discovery rate at 5%.

Handling of missing data and data below LOD

Missing values in the questionnaire were not imputed. For the biomarkers data below the limit of detection (LOD), imputation was performed based on existing suggestions for handling non-detect urinary measured concentrations data.¹¹ For outcomes that contained $<20\%$ values below the detection limit, values $<\text{LOD}$ were imputed as $\text{LOD}/2$ and for outcomes that contained $\geq 20\%$ values below detection, values $<\text{LOD}$ were imputed with regression on order statistics (ROS). With the ROS method, non-detect data are replaced based on a probability plot of detects. Outcomes with $>70\%$

values below detection, were used as binary variables in the primary, post-hoc and sensitivity analyses.

Baseline characteristics

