The change in outcomes (biomarkers of pesticide exposure and of oxidative stress) between the baseline and the end of the organic period was assessed with the percent change between the last sample of the conventional treatment period (before the start of the organic treatment) and the last urine sample of the organic treatment period. The percent change was estimated only for the participants who completed the full course of the organic treatment. A one-sample T-test was used to assess whether the percent change was significantly different than zero.

Overall change between conventional and organic period

The overall change in outcomes between the conventional and organic period was assessed using the overall difference in median levels. The conventional period consists of all conventional samples, including the baseline sample, and the organic period will consist of all organic samples for all participants, regardless of the duration for which they followed the organic treatment. The overall difference in the median levels of the outcomes between the conventional and the organic period was assessed using the unpaired T-test if the outcomes were normally distributed or using the non-parametric Wilcoxon test if the outcomes were non-normally distributed.

Primary analysis of outcomes

Linear mixed-effect regression models were used for continuous outcomes and logistic models for binary variables (i.e. those with >70% values below LOD), to account for the duration and the effect of treatment. To account for the clustering of participants within schools and the repeated measures within person, the models will include student-level and school-level random intercepts with unsupervised covariance matrix. Fixed effects were: the treatment condition (organic or conventional) and time (days of treatment, where time=0 was the start of the treatment). An interaction term for the treatment condition and time were considered and dropped when not meeting the threshold of p-value=0.05. The models were adjusted for the baseline value of the outcome in order to account for the background biomarker levels of the participant. The baseline sample was a conventional sample for both groups but it was not consecutive to the conventional phase due to the study design and, thus, it is indicative of each participants exposure prior to participation in the study

In all regression models, the continuous variables, other than time, were centred at the population means.

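### The SAP t-tests the percent change itself, the protocol puts the same test on log-transformed biomarkers, and neither defines the tested quantity; averaged percent changes would be biased upward

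*SAP*

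**What the plan says.** The SAP section on change between baseline and the end of the organic period compares two samples per child: the last conventional sample before the organic diet and the last organic sample. It expresses the comparison as a percent change and continues: "A one-sample T-test was used to assess whether the percent change was significantly different than zero". The population is restricted: "The percent change was estimated only for the participants who completed the full course of the organic treatment". That section mentions no logarithm, ratio or back-transformation.

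Protocol item 12 (Statistical methods) describes the same pair of samples, but there the percent change "was determined with one sample t-test for all biomarkers (log-transformed". The same sentence says that the separate conventional-versus-organic comparison "was determined using Wilcoxon test for all biomarkers (non-normal variables", so the biomarkers are regarded as skewed.

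The SAP also has a general rule under unadjusted and adjusted analyses: "If outcomes are not normally-distributed and the analyses require the normality assumption, then outcomes will be log-transformed (natural logarithm". The primary models are reported as geometric mean ratios (GMR) or odds ratios. No formula in either document links log values to the percent change.

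**The concern.** A percent change has a floor at -100% and no ceiling. A child whose value doubles contributes +100%, and a child whose value halves contributes -50%. Equal numbers of each average +25%, although nothing has changed on the ratio scale. Zero is therefore not the value that the average takes under no effect, and a t-test against zero rejects too often in the direction of an increase.

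The comparison is made for the pesticide metabolites and the oxidative stress markers, and it yields a percentage and a p-value that readers will set beside the GMRs. If it was computed as the SAP sentence reads, it could disagree with the primary model for purely arithmetical reasons, and the trial's expected reduction would be understated. If it was computed on logs, the SAP sentence misdescribes it.

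**Working it through.** **Inputs from the documents.** The sample size section uses "Assuming a power of 80% and a two-sided 5% significance level"; also "the within subject standard deviation of CRP was assumed to be 0.5", and a difference assumed "to be 0.1, based on other intervention studies". The stated result is 200 children.

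**Reproducing that figure.** n = (SD × (z₀.₉₇₅ + z₀.₈₀) / difference)² = (0.5 × (1.960 + 0.842) / 0.1)² ≈ 196.2, so 197. The noncentral t gives 199, and power at 200 is 80.4%. The figure reproduces, taking 0.5 as the SD of the paired difference. It concerns CRP and is not the SD of a log ratio of the trial's biomarkers, so it cannot size this point.

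**Assumptions.** The documents give neither the log-ratio SD (s) nor the number of completers. I vary s from 0.3 to 1.0 and completers over 100, 150 and 200, with a log-normal ratio.

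**Direction, without log-normality.** Let A be the conventional and B the organic value, both positive. If the diet does nothing and A and B are exchangeable, E(B/A) = E[(B/A + A/B)/2]. Since x + 1/x ≥ 2, this is at least 1, and it exceeds 1 whenever A and B differ.

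**Size, with log-normality.** ln(B/A) ~ Normal(ln GMR, s²), so the mean percent change = 100 × (GMR × exp(s²/2) − 1).

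- No effect, s = 0.3: exp(0.045) − 1 = +4.6%
- No effect, s = 1.0: exp(0.5) − 1 = +64.9%
- GMR 0.70, s = 0.5: 0.70 × exp(0.125) − 1 = −20.7%
- A 30% fall is cancelled exactly when exp(s²/2) = 1/0.70, that is s = √(2 × ln(1/0.70)) = 0.845

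**Rejection rates**, two-sided 5%, 20,000 simulated trials per setting; the three entries are for n = 100 / 150 / 200:

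| s | Mean % change, no effect | False significant increase | Mean % change, GMR 0.70 | Significant fall, raw percent | Significant fall, log difference |
|---|---|---|---|---|---|
| 0.3 | +4.6 | 28 / 40 / 53% | −26.8 | 100 / 100 / 100% | 100 / 100 / 100% |
| 0.5 | +13.3 | 60 / 80 / 91% | −20.7 | 99 / 99.9 / 100% | 100 / 100 / 100% |
| 0.7 | +27.8 | 85 / 96 / 99% | −10.6 | 38 / 48 / 57% | 99.9 / 100 / 100% |
| 0.845 | +42.9 | 93 / 99 / 99.9% | 0.0 | 7 / 6 / 5% | 99 / 99.9 / 100% |
| 1.0 | +64.9 | 97 / 99.7 / 100% | +15.4 | 0.6 / 0.3 / 0.1% | 95 / 99 / 99.8% |

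At s = 1.0 and GMR 0.70 the raw test also declares a significant increase in 10 / 17 / 25% of trials. The t-test on the log difference has about 2.5% false rejections in each direction in every row.

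**The case against.** The strongest reply is that the documents already put this test on the log scale. Protocol item 12 says so for the identical comparison, and the SAP's general rule logs non-normal outcomes when a method needs normality, as a t-test on skewed data arguably does. The natural reading is then a test of the mean log difference, back-transformed, as is done for the GMRs. On that reading none of the error rates above arise. This largely stands: a reader might infer from the SAP sentence that raw percent changes were in fact averaged and that the reported p-values are wrong, but the documents do not establish that.

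A reader might also infer that logging first means a percent change of logged values, (ln B − ln A)/ln A, which would depend on the unit of measurement. That formula is in neither document and should not be attributed to the plan.

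It can further be said that the mean individual percent change is a legitimate estimand with zero as its own null. That is true, but zero for that estimand is not the absence of a diet effect, nor GMR = 1, which is the question the trial asks.

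Finally, the comparison is secondary. The SAP reserves the primary analysis for the mixed and logistic models, and its false discovery rate control covers regression parameters of the primary and post-hoc analyses only. That stands too.

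What survives is that the SAP sentence, followed as written, gives a biased result. It does not agree with the protocol, and the valid quantity is left for the analyst to supply.

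**Conclusion.** The point holds as a conflict between the two documents with a real consequence under one of the two readings. If individual percent changes were averaged, no effect would show as a mean rise of about 5% to 65% and as a false significant increase in roughly 28% to 100% of trials. These sizes rest on log-normal ratios, an assumed log-ratio SD of 0.3 to 1.0, and an assumed 100 to 200 completers. The upward direction needs only exchangeable positive samples.

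It would be tempting to say that a true 30% fall disappears. That is so only near a log-ratio SD of 0.85 or more, a value the documents do not give. At 0.5 the fall is still found in at least 99% of trials, and at 0.7 in 38% to 57%.

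It would also be tempting to treat this as the trial's main result. The documents do not: it is a supplementary comparison in completers, and the primary mixed and logistic models are untouched. The log-normal figures do not describe 6-CN, for which the protocol reports 72% of values below LOD.

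**What to change.** Reconcile the SAP section with protocol item 12 by using one sentence in both, for example: *For each child compute d = ln(last organic sample) − ln(last conventional sample before the organic diet); test mean d = 0 with a one-sample t-test; report 100 × (exp(mean d) − 1) with its back-transformed 95% CI.* Add that individual percent changes are not averaged.

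State separately how, or whether, this comparison is made for 6-CN, since most of its values would be imputed.

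The cost is one sentence in each document. If log differences were used, the results stand and only the description changes. If percent changes were averaged, one table has to be re-run. No new data are needed.

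### The two sets of organic-versus-conventional change tests lie outside the SAP's false discovery correction and carry no descriptive label, so up to ten diet comparisons can be called significant at an uncorrected 5%

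*SAP*

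**What the plan says.** **The correction and its scope.** The SAP section on multiple testing adopts the Benjamini-Hochberg "method considering all the regression parameters of the primary and post-hoc analyses", with this decision rule: "Q-value <0.05 indicates statistical significance of an association after controlling the false discovery rate at 5"%. The section on levels of confidence and p values sets the general default: "The statistical significance level set will be at the 5% level", and tests are two-sided. Protocol item 12 contains no multiplicity rule.

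**The change tests.** Two SAP sections come before the one headed as the primary analysis of outcomes.

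- *Change between baseline and the end of the organic period* compares each child's last conventional sample before the organic diet with the last organic sample: "A one-sample T-test was used to assess whether the percent change was significantly different than zero".
- *Overall change between conventional and organic period* compares all conventional samples, including baseline, with all organic samples: "The overall difference in the median levels of the outcomes between the conventional and the organic period was assessed using the unpaired T-test", or the Wilcoxon test if the outcome is not normal.

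Protocol item 12 applies both to every biomarker. It says that percent change "was determined with one sample t-test for all biomarkers (log-transformed"), and it uses the Wilcoxon test for the difference in medians. The outcomes sections name five biomarkers: two primary (3-PBA, 6-CN) and three secondary (8-iso-PGF2a, MDA, 8-OHdG).

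**Labels.** Only the models listed as post-hoc are called ancillary. Where item 12 speaks of descriptive statistics, it means the children's characteristics.

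**The concern.** The change tests are not regression parameters, and they belong to neither the primary nor the post-hoc section. They are therefore outside the correction on both counts. They are still worded as significance tests, so the general 5% level applies to them by default.

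Each primary metabolite then has three tests of the diet effect: one judged by q < 0.05 and two judged by p < 0.05. A Benjamini-Hochberg q-value is never smaller than its raw p-value. The models that the SAP itself calls post-hoc therefore face a rule at least as strict as these tests on primary outcomes. The change tests also lack the child and school random effects of the primary model.

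At stake is what can be claimed beside the primary result. If the corrected model for 3-PBA or 6-CN misses q < 0.05, the plan as written still allows a significant diet effect to be reported on that metabolite from either change test.

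**Working it through.** The plan gives no error rate for these tests, so there is no figure of its own to reproduce. The inputs are the stated level and the count of tests.

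**1. Count.** 2 tests × 5 biomarkers = 10. Protocol item 12 gives 72% of 6-CN values below the limit of detection. The SAP makes such an outcome binary only in the primary, post-hoc and sensitivity analyses, so 6-CN appears to enter the change tests as imputed continuous data. If it were left out, 2 × 4 = 8. The two primary metabolites alone account for 2 × 2 = 4.

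**2. Expected false positives with no diet effect.** 10 × 0.05 = 0.5, whatever the correlation.

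**3. Chance of at least one, independent tests of exact 5% size.**

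- Ten tests: 1 − 0.95^10 = 40.1%
- Eight tests: 1 − 0.95^8 = 33.7%
- Four primary-metabolite tests: 1 − 0.95^4 = 18.5%

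**4. Allowing for correlation.** The tests share samples and children, so independence gives the high end. The documents give no correlations; those below are assumptions. The figures come from 400,000 simulated null sets of ten two-sided z-tests.

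| Correlation between biomarkers | Correlation between the two tests on one biomarker | Any p < 0.05, ten tests |
|---|---|---|
| 0 | 0 | 40% |
| 0 | 0.5 | 38% |
| 0.5 | 0.5 | 29% |
| 0.5 | 0.8 | 27% |
| 0.8 | 0.8 | 19% |

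If every correlation, including that between different tests on different biomarkers, is 0.8, the last row falls to 17%. For the four primary-metabolite tests the chance is 12% to 19%.

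**5. Allowing for a conservative unpaired test.** Each child can give three conventional samples (baseline plus two) and three organic samples. Let ρ be the correlation between samples from one child. With 3 + 3 samples from each of N children:

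- variance assumed by the unpaired test: 2σ²/(3N)
- true variance of the difference: 2σ²(1 − ρ)/(3N), because a constant child effect cancels
- true two-sided size: P(|Z| > 1.96/√(1 − ρ))

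This gives 2.8% at ρ = 0.2, 1.9% at ρ = 0.3 and 0.6% at ρ = 0.5.

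Take ρ = 0.3, so five tests have size 5% and five have size 1.9%. Under independence, 1 − 0.95^5 × 0.981^5 = 1 − 0.774 × 0.909 = 30%. Under the other settings in step 4 the chance falls as correlation rises, reaching about 14% with correlations of 0.8.

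**6. What a correction would do.** Benjamini-Hochberg at 5% over the ten tests as their own family brings the chance of any false positive to 3% to 5% in the same simulations.

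**7. Why the ten should not join the existing family.** Benjamini-Hochberg thresholds depend on every p-value in the family. Take five illustrative model p-values: 0.03, 0.2, 0.4, 0.5 and 0.6.

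- Alone, the smallest has q = 0.03 × 5/1 = 0.15.
- After adding ten change-test p-values of 0.001, it ranks 11th of 15 and q = 0.03 × 15/11 = 0.041. A non-significant model result becomes significant through near-duplicate tests that ignore clustering.
- The opposite also happens. Suppose the smallest of five model p-values is 0.008, with q = 0.008 × 5 = 0.04. Ten added p-values between 0.3 and 0.9 raise it to 0.008 × 15 = 0.12.

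**The case against.** **The hierarchy already exists.** Both documents head one analysis as primary, and it is the mixed or logistic model. That stands. A reader might infer that the trial's primary conclusion is inflated; the documents do not support this, because the model's q-values do not involve the change tests. What remains is that nothing states the standing of the change tests, while the SAP words the first of them as a test of significance.

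**The correction never claimed to cover every test.** This is also fair. The SAP states its family openly, and leaving non-primary tests uncorrected is a defensible choice when they are labelled as such. It would go too far to say that the SAP breaks its own promise. The gap is the missing label.

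**The error rates are overstated.** In part this stands. A reader might take 40% as the actual rate, but it needs ten independent tests, each of exact 5% size. The unpaired test on crossover data is probably conservative with respect to the child effect, which is why the lower range is given. School-by-period or seasonal effects could push its size the other way, and the documents do not allow that to be calculated.

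**Sensitivity models.** They too are not named in the correction's scope, so a reader might infer that they offer another uncorrected route to a claim. The SAP presents them as re-runs based on the primary analysis, and nothing in it says that they support separate significance claims. They form no part of this point.

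**Conclusion.** The point holds as a labelling and multiplicity gap outside the primary analysis. Up to ten diet comparisons (eight without 6-CN) are framed as significance tests at 5%, with neither correction nor descriptive label. They can be reported as significant when the corrected model for the same biomarker is not.

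With no diet effect, the chance of at least one false positive is about 19% to 40% if all tests have exact 5% size. It is about 14% to 30% if the unpaired test has a size of about 1.9%, which follows from an assumed child correlation of 0.3 and three samples per diet. Both ranges are well above 5%, and both rest on assumed correlations.

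The plan should be changed on this point, but the change does not touch the primary model or its conclusion.

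**What to change.** In the two SAP sections on change, and in Protocol item 12:

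1. State that the diet effect from the mixed or logistic model is the only confirmatory test for each biomarker.
2. Report the percent change and the difference in medians as descriptive estimates with 95% confidence intervals and no significance claim.
3. If p-values are kept, adjust them in a separate family. Do not add them to the existing Benjamini-Hochberg family, because that changes the q-values of the primary models.

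The cost is a few sentences of wording, plus intervals from data already being analysed. The downside is that these tests lose their significance claims.
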